8.1	CONFIDENTIALITY.....	12
8.2	SOURCE DOCUMENTS	12
8.3	CASE REPORT FORMS.....	12
8.4	RECORDS RETENTION	12
9	STUDY MONITORING, AUDITING, AND INSPECTING	12
9.1	STUDY MONITORING PLAN.....	12
9.2	AUDITING AND INSPECTING	13
10	ETHICAL CONSIDERATIONS	13
11	STUDY FINANCES	13
11.1	FUNDING SOURCE.....	13
11.2	CONFLICT OF INTEREST	13
11.3	SUBJECT STIPENDS OR PAYMENTS	13
12	PUBLICATION PLAN	13
13	REFERENCES	14

CONFIDENTIAL

List of Abbreviations

CRS	Chronic Rhinosinusitis
NO	Nitric Oxide
FESS	Functional Endoscopic Sinus Surgery
HUP	Hospital of the University of Pennsylvania
CRF	Case Report Form
AE	Adverse Event
SAE	Serious Adverse Event
IDS	Investigational Drug Service

CONFIDENTIAL

Study Summary

Title	Efficacy and Safety of Adjuvant Topical Irrigation in the Treatment of Acute Exacerbation of Chronic Rhinosinusitis Following Functional Endoscopic Sinus Surgery (FESS)
Short Title	Topical Irrigation Therapy for CRS
Protocol Number	821731
Phase	II
Methodology	Randomized, double-blinded, placebo-controlled clinical trial.
Study Duration	3 years for accrual and follow up (+1 year for data analysis)
Study Center(s)	Single-center: Dept. of Otorhinolaryngology at HUP
Objectives	To evaluate the physiological differences between quinine-saline vs sucrose octaacetate-placebo nasal irrigations in subjects with CRS (both with and without polyps) as well as allergic fungal sinusitis.
Number of Subjects	Number of subjects projected for the entire study: 100
Diagnosis and Main Inclusion Criteria	Chronic Rhinosinusitis post FESS
Study Product, Dose, Route, Regimen	Nasal instillation of quinine sulfate and saline solution using a 3cc syringe adopted with an atomizer.
Duration of administration	Total duration of drug product administration (including any open-label lead-in, if applicable) is twice/day for 28 days.
Reference therapy	Desroisiers et al. (2001) findings showed that topical quinine in saline nasal solution was comparable, if not better to topical tobramycin (a commonly used antibiotic) for treatment of bacterial sinusitis.
Statistical Methodology	Longitudinal linear mixed-effects models to evaluate pre- and post-treatment continuous outcome scores.

CONFIDENTIAL

1 Introduction

This document is a protocol for a human research study. This study is to be conducted according to US and international standards of Good Clinical Practice (FDA Title 21 part 312 and International Conference on Harmonization guidelines), applicable government regulations and Institutional research policies and procedures.

1.1 Background

Sinusitis is a common disorder accounting for an estimated 13 million physician office visits in the United States each year¹. The aggregated cost of sinusitis is approximately \$8 billion annually², affecting an estimated 16% of the population in the United States¹. Despite multiple attempted treatments, including an estimated 550,000 surgeries per year³, the disease continues to be a major health problem, both in expenditures and poor quality of life. Recent analysis of data from the National Ambulatory Medical Care Survey and the National Hospital Ambulatory Medical Care Survey from 2006 to 2010 showed that rhinosinusitis accounted for more outpatient antibiotic prescriptions in adults than any other diagnosis⁴.

Chronic rhinosinusitis (CRS) represents a considerable subset of this population and accounts for a significant portion of expenditures and the vast majority of surgeries. It is defined as signs and symptoms of sinusitis lasting more than 12 weeks^{5,6}. Unlike the organisms responsible for acute rhinosinusitis, difficult to treat bacteria such as *Pseudomonas aeruginosa*, *Staphylococcus aureus* and *Stenotrophomonas multiformia* are often offending pathogens in CRS⁷. Their prevalence increases in those patients who have already had sinus surgery and continue to get recurring sinus infections. *Staph aureus* and gram-negative organisms have been shown to account for roughly 60% of infections in those patients who have previously undergone endoscopic sinus surgery⁷.

Due to increasing drug resistance as well as the potential for biofilm formation, there has been an increasing pressure from both patients and clinicians alike to develop alternative treatments to systemic antibiotics. One commonly used alternative in patients who have had previous sinus surgery is topical saline irrigation with and without other topical preparations. Topical irrigations have much greater paranasal sinus penetration in post surgical patients⁸. Commonly used topical preparations include: saline alone or saline mixed with mupirocin, gentamicin, tobramycin, ceftazadine, betadine, manuka honey, baby shampoo, budesonide or mometasone⁹.

We have recently identified a novel arm of upper airway innate immunity mediated by bitter taste receptors¹⁰⁻¹⁵. When a subset of airway bitter taste receptors is activated they stimulate the respiratory epithelium to generate nitric oxide, an important component of sinus innate immunity that increases mucociliary clearance as well as diffuses into the mucus where it is bactericidal. A topical therapy to activate these taste receptors may help the sinuses clear infections through this natural innate defense mechanism. While we have identified multiple bitter compounds that stimulate this response, quinine piqued our interest as it activates multiple bitter taste receptors and has already been used in the human nose.

1.2 Investigational Agent

Quinine sulfate (USP Grade) as well as Sucrose Octaacetate (USP Grade, from Spectrum Pharmaceuticals, Nenderson, NV). Both are commonly used as agents to mimic a bitter taste in placebos at Penn IDS.

1.3 Preclinical Data

Using primary human sinonasal epithelial cells loaded with the intracellular dye DAF-FM we have screened multiple bitter tasting compounds^{12,13}. We have found that quinine stimulates robust NO production in a dose dependent manner that is mediated via T2Rs. Sucrose Octaacetate (used to wean babies off pacifiers) does not stimulate sinonasal epithelial cells to produce NO.

CONFIDENTIAL

Repetitive treatment (daily application) of Quinine (1mg/ml) to primary human sinonasal cultures does not demonstrate tachyphylaxis regarding NO production, nor demonstrates any cellular toxicity.

1.4 Clinical Data to Date

In a 2001 study by Desrosiers et al¹⁶, topical tobramycin was being evaluated for efficacy in medically recalcitrant bacterial sinusitis. In order to blind the control group, quinine was added to saline to mimic the bitter taste of tobramycin. Patients were treated with nasal solutions three times per day for 4 weeks. Interestingly, both treatment arms demonstrated clinical improvement, with the saline+quinine arm demonstrating comparable if not better efficacy to topical tobramycin with no adverse events reported in the study. These findings were surprising and “unexplained” to the authors at the time. We now believe that the quinine in their “control” group stimulated airway bitter taste receptors to stimulate sinonasal nitric oxide production to eradicate the infection. We should also mention that tobramycin does not stimulate NO production in primary human sinonasal epithelial cells.

Additionally, safety of quinine administration is further supported by a prior 1993 study that utilized quinine to determine compliance with nebulized tobramycin in the management of CF pseudomonas¹⁷. In this study the pharmacokinetics of inhaled tobramycin was evaluated. To assess compliance with the protocol both the tobramycin and placebo arms were spiked with quinine (1mg/ml) and urine quinine concentrations were checked. No adverse events were reported for the use of quinine in the airway.

Thus, we propose to repeat the Desrosiers study, but to instead evaluate quinine as a therapeutic agent, not a placebo, and directly compare quinine to saline (spiked with Sucrose Octaacetate). Truth be told, we stumbled onto the biologic effect of quinine in the search for a bitter compound to use in a randomized trial with another bitter compound. Surprisingly, quinine stimulated a more robust NO response than our original compound of interest (phenylthiocarbamide). Subsequently, we discovered the 2001 Desrosiers study that further supported the concept of quinine as a topical therapy for bacterial sinusitis.

1.5 Dose Rationale and Risk/Benefits

Our plan is to first study quinine against saline to determine efficacy and safety. The vast majority of patients with rhinosinusitis utilize low pressure / high volume (240mls) sinonasal lavage to cleanse the sinonasal cavity⁹. We propose to have the patients administer 6mls of quinine (1mg/ml) (same concentration that was used in the study mentioned above, which also activates NO production from human primary nasal cells *in vitro*) via a 3cc syringe with a mucosal atomizing device (MAD) on the tip. Patients will apply 3 mls to each nostril twice per day. Thus the patients will be exposed to a maximum of 12mls or 12.0 mg of quinine. In standard tonic water, quinine is 8.3mg/100mls and thus an 8oz glass of Canada Dry tonic water has 19.6mg of quinine. Thus, the maximum systemic exposure in our study (assuming ingestion of the total nasal administration) is less than drinking one glass of tonic water / day. To put this in context, the therapeutic range of quinine to treat malaria is 10mg/kg TID (2100mg for a 70kg individual) nearly 200 X the dose we are proposing.

We propose to enroll only patients who have had prior functional endoscopic sinus surgery (FESS) for two reasons: (1) better access to the sinonasal cavity to obtain microbiologic samples before, during and after the trial, and (2) patients with a marsupialized sinonasal cavity are not at risk for developing intra-orbital or intra-cranial complications from bacterial sinusitis, as a path of egress for the infection is widely patent into the nose.

2 Study Objectives

The overall objective of this study is to evaluate the efficacy of quinine nasal irrigations as a first line therapy for acute exacerbations of uncomplicated chronic rhinosinusitis following endoscopic sinus surgery.

2.1 Primary Outcome Variable(s)

CONFIDENTIAL

The primary outcomes variables are:

- Pre- and post-treatment endoscopically guided sinonasal microbiologic cultures
- Pre- and post-treatment nasal endoscopy scored with the Lund-Kennedy scoring system by a blinded investigator¹⁸.
- Pre- and post-treatment quality of life questionnaires (22-item Sinonasal Outcomes Test [SNOT-22]).
- The necessity for rescue oral antibiotics for persistent infection.

2.2. Secondary Outcome Variable(s)

The secondary outcomes variables are:

- Pre- and post-treatment Sniffin' Stick-12 (Burghart Instruments, Wedel, Germany) score.
- Pre- and post-treatment CT scan scored with the Lund-MacKay CT scoring system¹⁹ by a blinded investigator. The CT scans at pre and post will only be done if clinically indicated by the physician.
- Pre- and post-treatment microbiome analysis
- Pre-treatment taste test to determine bitter taste sensitivity

3 Study Design

3.1 General Design

- This is a Randomized, double-blinded, placebo-controlled protocol
- The duration of subject participation is approximately 12 weeks
 - (Week 0) Screening/Baseline:
 - Microbiome swab obtained
 - Sniffin' Stick-12
 - Nasal Endoscopy (Lund-Kennedy Score)
 - CT scan (Lund-MacKay CT Score) if clinically indicated.
 - SNOT-22 survey
 - Nasal Irrigation distributed (Week 0)
 - 4 week period of nasal irrigation administration (2 times a day)
 - (Week 4)
 - Microbiome swab obtained
 - Nasal Endoscopy (Lund-Kennedy Score)
 - Sniffin' Stick-12 Microbiology/traditional swab*
 - SNOT-22 survey
 - (Week 12) Return to clinic for assessment of durable changes:
 - Microbiome swab obtained
 - Sniffin' Stick-12
 - Microbiology/traditional swab*
 - SNOT-22 survey
 - CT scan (Lund-MacKay CT Score) if clinically indicated

* Microbiology/traditional swabs are part of routine care if pus is evident during routine clinical nasal endoscopy.

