3.2 Primary Study Endpoints

- Efficacy of quinine and saline irrigations compared to saline irrigations alone.
- Changes in quality of life (SNOT-22 questionnaire) (both composite and subscale scores)
- Nasal endoscopy (Lund-Kennedy Score)
- Alterations in microbiology recovered (as determined by sinus microbiology culture)
- Whether or not conventional antibiotics were needed to treat the infection during or following the irrigation trial (as prescribed as part of routine care)

CONFIDENTIAL

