4.1 Inclusion Criteria

1. Patients diagnosed with chronic rhinosinusitis, with and without polyps, as well as allergic fungal sinusitis
2. Patients who have undergone Functional Endoscopic Sinus Surgery (FESS)
3. Purulent drainage on nasal endoscopy
4. Male or female subjects, 18 years of age or older
5. Patients seen at the Dept. of Otorhinolaryngology clinic at HUP, a tertiary care clinic.

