4.3 Subject Recruitment and Screening

All study personnel will be appropriately trained and certified according to their role in the study and duties, including HIPAA and CITI training.

Subjects will be identified and approached as they present to clinic for their routine treatment for chronic rhinosinusitis. Subjects will be brought into a private clinical examination room where a clinical research nurse will explain the protocol in detail. Subjects will have the time to ask and have questions answered about the research prior to signing the consent form.

Patients interested in enrolling in the study will be instructed on how to administer the solutions using a 3cc syringe with an atomizer and have the opportunity to trial this technique with isotonic buffered saline under direct supervision of the treating physician or research coordinator. Patients who feel that they can adequately self-administer the solution will be asked to participate in the study.

Subjects who withdraw or are otherwise not interested in the protocol will have access to the ENT clinic for their regular care. They will be reminded that their care (and if applicable, employment, or student status at Penn) will in no way be affected by their decision to participate in the protocol or not.

As per FDA recommendation, the first 10 patients enrolled into the study will be placed into the treatment arm, and will not be randomized. The purpose of this is to make sure that the treatment is efficacious enough to rationalize going forward with the trial. This will not affect the ICF, as the patient will not be aware of this forced assignment into the treatment arm (i.e. they will still be blinded to their assignment).

CONFIDENTIAL

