4.4 Early Withdrawal of Subjects

4.4.1 When and How to Withdraw Subjects

Subject may be withdrawn from the study prior to the expected completion of the protocol if the subject fails to adhere to protocol requirements, subject withdraws consent, or symptoms of acute rhinosinusitis exacerbation persist. Subjects will return to routine clinical care at that point.

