4.4.2 Data Collection and Follow-up for Withdrawn Subjects

Even though subjects may be prematurely withdrawn from the study, it is imperative to collect infection data (microbiology swabs) or symptomatic data. Such data is important to the integrity of the final study analysis since early withdrawal could be related to the tolerability profile or the ineffectiveness of the therapy. If a subject withdraws consent to participate in the study, attempts should be made to obtain permission to follow up with the subject's CRS for the duration of the 12-week follow-up period. Subjects with incomplete/missing data will not be included in the analysis.

5 Study Drug

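### The Section 3.1 footnote can be read as limiting post-treatment cultures, a primary outcome, to visits where pus is seen, while Section 6 schedules them at every visit without condition

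*Combined protocol and SAP*

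**What the plan says.** Section 2.1 lists "Pre- and post-treatment endoscopically guided sinonasal microbiologic cultures" among four primary outcomes, and Section 3.2 repeats change in culture findings as a primary endpoint.

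The schedule is given twice:

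- **Section 3.1** lists a microbiology swab at weeks 4 and 12, each with an asterisk. The footnote reads "Microbiology/traditional swabs are part of routine care if pus is evident during routine clinical nasal endoscopy". This outline shows no culture at week 0 and no endoscopy at week 12.
- **Section 6** (table) lists culture and endoscopy at weeks 0, 4 and 12 in the Clinical Care column, with no condition on either. Section 6.1 describes the Visit 1 culture as routine. Sections 6.2 and 6.3 repeat the Visit 1 procedures and make an exception only for CT.

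Four other places bear on the point. Section 4.1 requires "Purulent drainage on nasal endoscopy" at entry. Section 4.4.2 says of withdrawn subjects that "it is imperative to collect infection data (microbiology swabs) or symptomatic data", yet ends by leaving subjects with incomplete data out of the analysis. Section 6.5 lets the mixed model use all available data provided missingness is neither excessive nor patterned. Section 6.6 analyzes everyone randomized.

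**The concern.** Because pus is an entry criterion, every subject meets the footnote's condition at week 0. The condition can therefore bite only after treatment, when pus is a sign that the drug is meant to clear. If clinic staff follow 3.1, a subject whose pus has gone has no post-treatment culture, and one whose pus persists has one. A comparison of cultures between arms would then be made among subjects chosen by their response.

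The analysis text does not repair this. Such missingness would be patterned by design, which is the case that Section 6.5 sets aside without offering an alternative. The closing sentence of Section 4.4.2, read literally, could remove the subjects who cleared. It does not say that the exclusion applies outcome by outcome, so they could be lost from other outcomes as well. That also sits badly with Section 6.6. No section says how a visit without pus counts for the culture endpoint.

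**Working it through.** **The plan's own figure.** The only computed design figure is 32 per group for a 95% CI half-width of 10 on SNOT-22 with SD 20 (Section 6.4). The normal formula gives n = 2 × (1.96 × 20 / 10)² = 30.7. With the t distribution the half-width is 10.16 at n = 31 and 9.995 at n = 32, so 32 reproduces. It does not concern culture. The documents give no rate of pus or of positive culture.

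**The texts side by side.**

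| Item | Section 3.1 | Section 6 |
|---|---|---|
| Culture, week 0 | not listed | listed, no condition |
| Culture, weeks 4 and 12 | listed, footnote on pus | listed, no condition |
| Endoscopy, week 12 | not listed | listed |
| Culture when no pus is seen | not addressed | not addressed separately; column is Clinical Care |

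**What selection on pus could do (illustration; every rate is assumed).** Treat culture as positive or negative, which Section 3.2 does not state. In each arm let s be the share with pus at the visit, p the positivity with pus and q the positivity without pus. Then:

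- positivity in all subjects = s·p + (1 − s)·q
- positivity in swabbed subjects only = p

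Differences are quinine minus placebo, in percentage points.

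| Case | s | p | q | All subjects | Swabbed only |
|---|---|---|---|---|---|
| A | 30% v 60% | 80% both | 0% both | 24 − 48 = −24 | 0 |
| B | 30% v 60% | 80% both | 50% both | 59 − 68 = −9 | 0 |
| C | 30% v 60% | 80% both | 80% both | 80 − 80 = 0 | 0 |
| D | 30% v 60% | 60% v 85% | 10% both | 25 − 55 = −30 | −25 |
| E | 50% both | 80% both | 10% v 50% | 45 − 65 = −20 | 0 |
| F | 50% both | 60% v 85% | 10% both | 35 − 47.5 = −12.5 | −25 |

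A and B hide a difference, C has none to hide, and D is barely distorted. E is distorted although pus persists equally in both arms. F, which joins the persistence of E to the positivity of D, overstates the all-subject difference.

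**Loss of information in case A.** Section 4.3 says that "the first 10 patients enrolled into the study will be placed into the treatment arm, and will not be randomized". If those 10 are among the 100 and the rest split evenly, each arm has (100 − 10) / 2 = 45. Expected swabs are 45 × 0.30 = 13.5 and 45 × 0.60 = 27, or 40.5 of 90, so 55% of cultures would be absent. The Newcombe 95% CI for the swabbed-only difference of 0 is then −28.7 to +22.7 points.

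**The case against.** The best reply is that the footnote only sorts swabs into routine care and research. It does not say that no swab is taken when pus is absent. Where the protocol means to restrict a procedure it does so openly, as with CT in Section 2.2: "The CT scans at pre and post will only be done if clinically indicated by the physician". Sections 6 to 6.3 are the detailed procedures and attach no condition to culture. Section 4.4.2 presses for swabs even after withdrawal. Section 3.1 is visibly an incomplete outline. The trial has one center, so sites cannot diverge in how they read it.

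Most of this stands, and the benign reading is the more likely one. It does not close the gap. If culture is routine care when pus is seen, and Section 6 places culture under clinical care, the text still does not settle whether a subject without pus is swabbed, and no scoring rule covers that visit.

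Four stronger readings are tempting, and the documents do not support them:

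- *The plan definitely restricts cultures to visits with pus.* Section 6 says otherwise.
- *Absent cultures could not be told apart from missed visits.* Section 8.3 requires missing items to be explained, with separate codes for not done and not applicable, and Section 6 schedules endoscopy at each visit. The reasons should be recoverable.
- *The other primary outcomes are safe.* Section 4.4.2 could exclude a subject from them too, and 3.1 followed literally has no week 12 endoscopy.
- *Equal persistence of pus in the two arms removes the problem.* Case E shows that it need not.

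**Conclusion.** The point holds as an unresolved conflict with a conditional consequence. Sections 3.1 and 6 differ on whether post-treatment culture depends on pus. If 3.1 is followed, a primary outcome is observed only in subjects selected on a post-randomization response, and Section 4.4.2 could compound this by dropping subjects who cleared.

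Neither the size nor the direction of any bias can be derived from the documents. The 24-point loss in case A rests wholly on assumed rates, chiefly that positivity with pus is the same in both arms and that positivity without pus is nil. Section 1.1 describes a bactericidal mechanism, so equal positivity with pus is not an obvious default.

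This should be fixed, with medium confidence, since the benign reading may be what was intended. The case for acting is that a culture not taken cannot be recovered later.

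**What to change.** 1. State that the Section 6 schedule governs. Remove the pus condition from the 3.1 footnote for study visits, and add the week 0 culture and week 12 endoscopy to 3.1. Culture is then taken at weeks 0, 4 and 12 whether or not pus is seen.
2. State in Section 4.4.2 that a visit without pus, or without a swab, is not a reason to exclude a subject from the analysis.
3. If a visit still has no culture because no pus was seen, record that reason under Section 8.3. Report it as its own category by arm among all randomized subjects.
4. For such visits, vary the assumed positivity without pus in a sensitivity analysis, and label any swabbed-only comparison as descriptive.

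The first two items are wording, and they add no procedure that Section 6 does not already list. The cost is that swabs taken without pus may need to be listed as research in the Section 6 table and covered by the consent and the budget. The last two items need only a coded reason and a short addition to Section 6.5. No replacement endpoint is needed.
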